2.1.2. Analysis Visits

In general, AVISIT will be derived as the day of a scheduled visit, assessment or self-assessment as recorded in the respective SDTM, including the safety follow-up visit and day 28 final study visit (e.g. 'Day 4'). AVISITN will be the numeric counterpart (e.g. for 'Day 4' AVISITN will be 4). The AVISIT for scheduled measurements before first intake will be set to 'Screening' with AVISITN = -1. For specifications on the baseline record and endpoint record see Section 2.5.

For post-baseline assessments of the Daily Activities Resumption (Return to daily activity), Patient Global Impression of Severity (PGIS), Patient Global Impression of Change (PGIC) and

the European Quality of Life 5 Dimensions (EQ-5D) questionnaires, AVISIT and AVISITN will be derived from the number of days in the study relative to the start of study treatment (reldy, see Section 2.4). Post-baseline assessments taken from 00:00 until 02:00 will be assigned to the day before (e.g. a recording on Day 4 at 01:00 will be assigned AVISIT= Day 3).

2.1.3. Analysis Timepoints

For parameters that were assessed more than once daily, the analysis timepoint (ATPT) will be the timepoint as reported in the database. In case there are multiple records per planned timepoint take the last in time.

For hospitalized subjects we expect 3 assessments per day. If the timepoint is missing but the date time is known, then we impute as follows:

If date time is within [00:00, 11:00] then allocate the morning timepoint

If date time is within [11:01, 16:00] then allocate the midday timepoint

if date time is within [16:01, 23:59] then allocate the evening timepoint

For subjects that are discharged we expect only 1 vital sign assessment. Therefore in case the timepoint is filled in, we set it to empty.

For NEWS2, select for each of the parameters one record per timepoint as described above. The date and time of the NEWS2 will be derived from the last date time of each of the parameters and this will be used to allocate the NEWS2 to a phase. A subject received oxygen at the planned timepoint if the date time of the oxygen saturation measurement falls within the period that the subject received supplemental oxygen.

2.1.4. Use of Records per Analysis Visit and Timepoint

To ensure only one record is used per analysis visit for the Return to daily activity and PGIS questionnaires only one questionnaire should be selected for analysis. Following rules should be followed to select the questionnaire.

1. The questionnaire latest in time is used.
2. If more than one questionnaire is still selected, the questionnaire with the highest sequence number is used.

To ensure only one record is used per analysis visit for the PGIC and EQ-5D questionnaires the following rules should be followed to select the questionnaire.

Listed below (Table 2) are the visit windows and the target days for each visit where PGIC and EQ-5D are recorded. The reference day is Study Day 1, the date of first intake of study drug.

1. If a subject has 2 or more actual visits in one visit window, the visit closest to the target day will be used as the protocol visit for that visit window.
2. If 2 actual visits are equidistant from the target day within a visit window, the later visit in time is used.

Table 2: Visit Windows for PGIC and EQ-5D

Scheduled Visit Number	Time Interval (label on output)	Time Interval (Day)*	Target Time Point (Day)
6	Day 6	[2 to 10]	6
14	Day 14	[11 to 20]	14
28	Day 28	[21 to 38]	28
For subjects on extended treatment:			
14	Day 14	[11 to 16]	14
19	Day 19	[17 to 22]	19
33	Day 33	[23 to 38]	33

*Relative to Study Day 1

2.1.5. Unscheduled Assessments

In general, all scheduled assessments after first administration of study drug will be used. Unscheduled assessments will not be used in descriptive statistics or any per-time point analysis, but will be shown in listings as applicable. Pre-dose unscheduled assessments will be taken into account for baseline determination and post first dose unscheduled assessments will be taken into account for worst-case determination.

For PRO assessments, both scheduled and unscheduled assessments will be taken into account to determine which assessment will be used per analysis visit / timepoint as described in Section 2.1.4.

For time to response endpoints, recordings taken at unscheduled visits will be taken into account unless indicated differently.

2.2. Analysis Sets

2.2.1. All Randomized Analysis Sets

2.2.1.1. All Randomized Analysis Set (RAND)

All randomized subjects with a randomization date time at or before the date time of first intake of study drug, or with a randomization date time and no study drug intake.

2.2.1.2. Randomized and/or Treated Analysis Set (RT)

All randomized subjects and/or all subjects who received at least 1 dose of study drug. The Randomized and/or Treated Analysis Set (RT) will be used in all listings unless specified otherwise for a specific display.

2.2.2. Efficacy Analysis Sets

Efficacy will be analyzed on the intent-to-treat infected (ITT-i) set and by randomized treatment. The primary efficacy endpoint will also be analyzed on the Per Protocol set. The primary efficacy endpoint and the six most important secondary endpoints (all endpoints included in the hierarchical

testing procedure at the final analysis) will also be analyzed on the intent-to-treat non-infected (ITT-ni) set and by randomized treatment.

2.2.2.1. Intent-To-Treat infected (ITT-i) set

All subjects from the RAND analysis set who receive at least 1 dose of study drug and who have a confirmed infection with influenza A. Confirmation of Influenza A infection will be obtained from virology data. If there are no virology data available at the final analysis, then a subject will be excluded from the ITT-i set. Analysis on the ITT-i set will be analyzed as randomized.

A subject is considered to have a confirmed infection with influenza A if he/she has:

- at least one positive PCR result from central lab testing at baseline or pre-baseline;

else

- at least two positive PCR results from central lab testing post-baseline;

else

- at least one positive result from local lab testing for influenza A at baseline or pre-baseline, provided that no central lab testing is available at baseline or pre-baseline.

Note: viral load (PCR) results from central lab testing recorded as ‘TARGET NOT DETECTED’ will be considered as negative, all other non-missing results as positive (i.e. between LOD and LOQ, or quantifiable (above LOQ)).

Note: If no viral load measurement is available prior to first study drug intake then the first viral load result from the central lab testing obtained up to and including 30 minutes after first dose of study drug will be considered as the baseline assessment. If no baseline central lab measurement is available, the first viral load result from the local lab test obtained up to and including 30 minutes after first dose of study drug will be considered as the baseline local test assessment in case no local lab test is available at baseline or pre-baseline.

Note: viral load results from the central lab testing obtained from leftover samples from the local virology test will be considered in determining confirmed infection with influenza A.

2.2.2.2. Per Protocol Set (PP)

All subjects in the ITT-i set without major protocol deviations that may have an impact on the efficacy analysis.

Decisions regarding which subjects are included in the per protocol set will be made before database lock on following criteria. Subjects will be included in the PP set in case:

- Subjects missed at most 3 doses in total or at most 2 consecutive doses. On the day of randomization or the next day at least one dose needs to be taken.
- The actual treatment must be the same as the planned treatment
- No unblinding may have taken place

- Subjects may not violate inclusion criteria 2,3,4 and 6 and exclusion criteria 1, 6, 9, 12 and 13.
- Influenza antiviral as part of the SOC was started no later than the day of first study drug intake,
- Subjects did not switch to another influenza antiviral as a part of the SOC

Inclusion/Exclusion	Criterion number	Description
Inclusion	2	Tested positive for influenza A infection after the onset of symptoms, using a rapid influenza diagnostic test (RIDT) or, if available, a PCR-based or other rapid molecular diagnostic assay.
Inclusion	3	Requires hospitalization to treat influenza infection and/or to treat complications of influenza infection (eg, radiological signs of lower respiratory tract disease, septic shock, central nervous system [CNS] involvement, myositis, rhabdomyolysis, acute exacerbation of chronic kidney disease, severe dehydration, myocarditis, pericarditis, ischemic heart disease, exacerbation of underlying chronic pulmonary disease, including asthma, chronic obstructive pulmonary disease [COPD], decompensation of previously controlled diabetes mellitus), including subjects admitted to the ICU. Note: for the purpose of the protocol, subjects admitted under “observation” status with an anticipated length of stay beyond 24 hours are eligible for enrollment.
Inclusion	4	Enrollment and initiation of study drug treatment \leq 96hours after onset of influenza symptoms.
Inclusion	6	Having a screening/baseline NEWS2 of \geq 4.
Exclusion	1	Received more than 3 doses of influenza antiviral medication (eg, OST or zanamivir), or any dose of RBV within 2 weeks, prior to first study drug intake. Received IV peramivir more than 1 day prior to screening.
Exclusion	6	Severely immunocompromised in the opinion of the investigator (eg, known cluster of differentiation 4 ⁺ [CD4 ⁺] count $<$ 200 cells/mm ³ , absolute neutrophil count $<$ 750/mm ³ , first course of chemotherapy completed within 2 weeks prior to screening, history of stem cell transplant within 1 year prior to screening, history of a lung transplant).
Exclusion	9	Taken any disallowed therapies as noted in the Protocol, pre-study and concomitant therapy before the planned first dose of study drug.
Exclusion	12	Subject has any condition for which, in the opinion of the investigator, participation would not be in the best interest of the subject (eg., compromise the well-being) or that could prevent, limit, or confound the protocol-specified assessments (eg, subject is unable to swallow medication tablets outside the hospital setting), with the exception of ePRO completion (see the protocol) ie, if a subject is not able to complete ePRO, the subject is still allowed to be enrolled in the study.
Exclusion	13	Subject has presence of any pre-existing illness, clinically significant laboratory abnormalities, ECG findings, or physical examination findings that, in the opinion of the investigator, would place the subject at an unreasonably increased risk through participation in this study. The investigator should consider the laboratory parameter criteria for study drug discontinuation when screening a subject for enrollment.

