6. DOSAGE AND ADMINISTRATION

During the treatment period, all subjects will receive study drug in a 1:1 ratio in 1 of the 2 treatment arms shown in the table below. Depending on the time of screening/enrollment, subjects will receive 1 dose (evening) or 2 doses (morning and evening) of study drug on Day 1. Subjects may delay or bring forward administration of the second dose (by no more than 4 hours) only if the nominal timing for this second dose falls in the middle of the night. For subjects who receive only 1 dose of pimodivir or placebo on Day 1 (evening), dosing should continue until the morning of Day 6 so that all subjects receive 10 doses in total.

Subjects who are eligible for the blinded extension arm will receive study drug as described in the table below. Subjects will receive 1 dose (evening) or 2 doses (morning and evening) of study drug on Day 6. For subjects who receive the first dose of study drug in the second treatment course in the evening of Day 6, dosing should continue until the morning of Day 11 so that the subject receives 10 doses in total during the second treatment course.

Study-site personnel will instruct subjects on how to store study drug for at-home use as indicated for this protocol.

No post-study medication is provided as part of this protocol.

	Treatment Arm 1	Treatment Arm 2	Treatment Extension Arm 1^a	Treatment Extension Arm 2^a
Test Article(s)	Pimodivir (Day 1 through Day 5) + SOC treatment ^{b,c}	Placebo (Day 1 through Day 5) + SOC treatment ^{b,c}	Pimodivir (Day 6 through Day 10) + SOC treatment ^{b,c}	Placebo (Day 6 through Day 10) + SOC treatment ^{b,c}
Description	300 mg tablet	Placebo tablet	300 mg tablet	Placebo tablet
Dose per Delivery	Day 1 to Day 5 600 mg pimodivir (2 tablets)	Day 1 to Day 5 Placebo (2 tablets)	Day 6 to Day 10 600 mg pimodivir (2 tablets)	Day 6 to Day 10 Placebo (2 tablets)
Frequency	Bid	Bid	Bid	Bid
Total Daily Dose	1,200 mg	NAP	1,200 mg	NAP
Delivery Method^d	Oral	Oral	Oral	Oral
Food/Fasting Requirement	No food requirements	No food requirements	No food requirements	No food requirements

Abbreviations: bid: twice daily; NAP: not applicable; SOC: standard-of-care.

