4.3. Treatment Compliance

Treatment compliance for pimodivir/placebo is calculated as the actual number of doses taken, as a percentage of the planned number of doses. The actual number of doses taken will be derived from the drug accountability information (DA domain) as the amount of drug dispensed minus the returned amount (in case both amounts are known, otherwise treatment compliance will be missing)

To differentiate between the compliance during the planned treatment subperiod and the planned treatment extension subperiod, the date of dispensing the tablets will be compared with the treatment extension start date (DS Domain). If the drug is dispensed before the treatment extension

start date it will be used for the compliance of the treatment subperiod. If the drug is dispensed on or after the treatment extension start date the amount will be used for the compliance of the treatment extension subperiod.

For placebo or pimodivir the actual number of doses needs to be divided by 2 as the study uses 300 mg tablets. For subjects without treatment extension the planned number of study drug is 20 tablets of placebo or pimodivir hence the planned number of doses per study drug equals 10 doses. For subjects with treatment extension the planned dose is doubled. Note that the planned number of doses is irrespective of whether the subject discontinued during the treatment phase.

Dosing compliance will be summarized descriptively in the treatment phase and per subperiod and by discontinuing the trial during the treatment period (Yes, No).

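### The per-protocol dose rule joins its two limits with *or*, so read literally it keeps a subject who missed 6 of 10 doses and drops one who missed 4

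*SAP*

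**What the plan says.** SAP 2.2.2.2 first describes the PP set in general terms: "All subjects in the ITT-i set without major protocol deviations that may have an impact on the efficacy analysis". It then turns this into a list introduced by "Subjects will be included in the PP set in case". The first item is the dosing condition, "Subjects missed at most 3 doses in total or at most 2 consecutive doses", followed in the same item by "On the day of randomization or the next day at least one dose needs to be taken". The other items concern treatment received, unblinding, named eligibility criteria and influenza antivirals in the standard of care.

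The number of planned doses comes from SAP 4.3: "hence the planned number of doses per study drug equals 10 doses". The same section adds "For subjects with treatment extension the planned dose is doubled" and "Note that the planned number of doses is irrespective of whether the subject discontinued during the treatment phase". Protocol section 6 agrees on the length of the course: after an evening start, "dosing should continue until the morning of Day 6 so that all subjects receive 10 doses in total".

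Protocol 11.1 also defines the PP set but gives no dose threshold. SAP 2.2.2 and Protocol 11.1 both say that the primary endpoint will be analyzed on the PP set in addition to ITT-i.

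**The concern.** In an exclusion rule, *or* between two violations is strict. In an inclusion rule, *or* between two limits is lenient. Here a subject leaves the PP set on dosing grounds (the early-dose sentence aside) only by breaking both limits at once, with more than 3 doses missed and at least 3 of them in a row. The limit on the total does not bind anyone whose misses are scattered. The limit on consecutive misses does not bind anyone with exactly 3 misses.

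What is at stake is the meaning of the PP result. If its dosing criterion can admit subjects who missed most of the course, agreement between the PP and ITT-i results says less than it appears to. There is also a programming risk: membership must be settled before database lock, and someone coding the rule must either follow the text or guess that both limits were intended.

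**Working it through.** **Inputs.** Ten planned doses (SAP 4.3); limits of 3 missed in total and 2 missed in a row, joined by *or*, plus one dose on the day of randomization or the next day (SAP 2.2.2.2); at least one dose taken, as the ITT-i definition requires (SAP 2.2.2.1).

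**The plan's own figure.** 5 days × 2 doses = 10, and 20 tablets ÷ 2 per dose = 10. This reproduces.

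**Most misses with no run of 3.** In *n* dose slots, each block of three needs at least one taken dose, so the maximum is *n* − floor(*n*/3).

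- *Count from first intake.* Dose 1 is taken by definition, leaving 9 slots: 9 − floor(9/3) = 6. Example, with T taken and M missed: TMMTMMTMMT. That is 4 of 10 doses, or 40% of the course.
- *Count from randomization.* All 10 slots are open: 10 − floor(10/3) = 7. Example: MTMMTMMTMM, or 30% of the course. Only four seven-miss patterns qualify. All four begin with a missed first dose, and all four satisfy the early-dose sentence.

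**Enumeration of all taken/missed patterns, early-dose sentence applied, count from first intake:**

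| Missed | Possible patterns | Admitted with *or* | Admitted with *and* |
|---|---|---|---|
| 3 | 84 | 84 | 77 |
| 4 | 126 | 90 | 0 |
| 5 | 126 | 51 | 0 |
| 6 | 84 | 10 | 0 |
| 7 | 36 | 0 | 0 |

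These are counts of possible sequences. They show what the rule permits, not how many subjects will follow such a sequence.

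**Ordering of subjects.** TTTTTTMMMM has 4 missed, all in a row. It fails both limits and is excluded. TMMTMMTMMT has 6 missed with a longest run of 2. It meets one limit and is included. The less adherent subject stays. This comparison assumes that doses not taken after stopping count as missed, as in the compliance rule of SAP 4.3; section 2.2.2.2 does not say so itself.

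**Extension.** With 20 planned doses, the same formula gives 1 taken dose followed by 19 slots: 19 − floor(19/3) = 13 missed. If all slots are open it gives 20 − floor(20/3) = 14. The PP rule does not say which course it covers.

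**With *and*.** The most a PP subject can miss is 3, and a subject whose 3 misses are consecutive is also excluded.

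**The case against.** The strongest reply is that both limits were plainly meant to hold. Under the literal reading the total limit does almost no work: among subjects with 3 or fewer misses, it matters only for 3 in a row. The opening sentence about major deviations points the same way. This is a fair reading of intent, but that sentence contains no dose number and the listed criteria are what decide membership. The text still needs correcting.

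Three further points stand and limit the finding. First, a reader might infer that 7 missed doses are admitted without qualification. Every seven-miss pattern starts with a missed first dose, whereas Protocol 9.1.2 and SAP 2.4 anchor study days at first intake and Protocol section 6 shifts the course so that 10 doses are still given. The early-dose sentence lends some support to a count from randomization, so 7 remains possible, but only on that basis. Second, a reader might take the number of admitted patterns as the size of the problem. Neither document gives an expected frequency of scattered misses, and early stopping of the initial course produces one unbroken run: anyone who stops with 4 or more doses left is excluded even under *or*. Third, a reader might conclude that the PP analysis is worthless or that the trial's main conclusion is at risk. The primary analysis is on ITT-i (SAP 5.2.1), the estimand handles treatment discontinuation by a treatment policy strategy (SAP 5.2.2), and the PP set has no place in the testing sequence (SAP 5.1.1).

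**Conclusion.** The rule is wrong as written. Followed literally, it admits a subject who missed up to 6 of the 10 initial doses, or 7 if doses before first intake count as missed, provided no more than 2 were missed in a row. It also excludes a subject who took the first 6 doses and stopped, on the assumption that doses after stopping count as missed. Nothing else in the protocol or SAP supplies a dose minimum that would prevent this.

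The consequence is a weaker supplementary PP analysis of the Day 6 endpoint. Alpha, power and the primary estimate do not change. How many subjects would be misclassified cannot be worked out from the documents and may be small. The correction is worth making because it is easy and because PP membership has to be fixed before database lock.

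**What to change.** In SAP 2.2.2.2:

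1. Replace *or* with *and*, so that both limits must hold: at most 3 of 10 doses missed and no more than 2 missed in a row.
2. Apply the rule to the initial 10-dose course. Planned doses double with extension, and extension doses follow the course that precedes the Day 6 endpoint, so misses among them should not decide membership of a Day 6 analysis.
3. State whether the count starts at randomization or at first intake, and whether doses not taken after early stopping count as missed.

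The first change is one word and the others a sentence each. The cost is a slightly smaller PP set. Only the definition of an analysis set changes; dosing and patient management do not.

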2.2.2.3. Intent-To-Treat non-infected (ITT-ni) Set

All subjects from the RAND analysis set who receive at least 1 dose of study drug and who do not have a confirmed infection with influenza A.

2.2.3. Safety Analysis Set

2.2.3.1. Safety Set or All Subjects Treated (AST)

All safety endpoints will be evaluated on the Safety population, consisting of all subjects who received at least one dose of study drug and will be analyzed by treatment arm as treated.

2.2.4. Pharmacokinetics (PK) Analysis Set

The PK analysis set is defined as subjects who have received at least 1 dose of pimodivir and have at least 1 valid blood sample drawn for PK analysis.

2.2.5. Pharmacodynamics (PD) Analysis Set

The PD analysis set is defined as all subjects in the PK analysis set for whom at least one PK parameter could be derived.

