No genotoxicity (mutagenicity, in vitro chromosomal aberration, or mammalian erythrocyte), phototoxicity (in vitro), or safety pharmacology (battery of in vitro studies designed to evaluate effects of pimodivir against multiple cellular targets and a battery of in vivo cardiovascular, central nervous system, and respiratory systems) liabilities have been identified for pimodivir. There were no toxicological effects in acute studies in mice and rats at doses up to 1,000 mg/kg. The no observed adverse effect level (NOAEL) in 14-day, repeat-dose toxicology studies was 100 mg/kg/day in rats and 150 mg/kg/day in monkeys. These doses correspond to animal to human exposure multiples (AUC from time 0 to 24 hours after dosing [AUC_{24h}] basis) of 41-fold and 24-fold in male and female rats, respectively, and 2-fold and 4-fold in male and female monkeys, respectively, based on a clinical dose of 600 mg bid for 5 days. When using the exposures measured in the 63623872FLZ2002 study (600 mg pimodivir bid in subjects at steady-state), these doses correspond to animal to human exposure multiples (AUC_{24h} basis) of 17-fold and 10-fold in male and female rats, respectively, and 0.7-fold and 1.6-fold in male and female monkeys, respectively. Although exposure ratios vs the NOAEL in monkeys are small, all adverse effects seen at the medium dose of 250 mg/kg/day show recovery after dosing and are monitorable in the clinic. At oral doses of 250 mg/kg/day and above, specific organ toxicity

(liver, kidney, bone marrow, spleen, and lymph nodes) and other toxicological findings were noted in rats and monkeys. When rats were dosed at 50, 100, or 250 mg/kg/day for 3 months, the NOAEL was set at 100 mg/kg/day, which corresponds to animal to human exposure multiples of 12-fold in males and 15-fold in females (multiple vs Study 63623872FLZ2002). At 250 mg/kg/day, body weight gain was decreased in both sexes. Additionally, minor alterations were seen in red blood cell (RBC) parameters. Full recovery of the adverse effects was noted at the end of the 1-month recovery period. The NOAEL in 14-day continuous IV infusion studies was 180 mg/kg/day in rats and 40 mg/kg/day in monkeys. Pimodivir exposure at the NOAEL in the IV studies was in the same range (AUC) or lower (C_{max}) than at the NOAEL in the oral toxicity studies.

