11.1. Analysis Sets

The efficacy endpoints will be analyzed on the Intent-to-Treat-infected (ITT-i) and by randomized treatment. The ITT-i set consists of all subjects who were randomized and treated and had a confirmed influenza A infection.

The primary endpoint will also be analyzed on the Per Protocol set, consisting of all subjects in the ITT-i set without major protocol deviations that have an effect on efficacy and who were not prematurely unblinded during the study.

All safety endpoints will be evaluated on the Safety population, consisting of all subjects who received at least one dose of study drug and will be analyzed by treatment arm as treated.

Pharmacokinetic data will be evaluated on subjects in the ITT-i set who received pimodivir. Subjects will be excluded from the population PK analysis if their data do not allow for accurate assessment of the PK parameters (eg, incomplete administration of the study drug; missing information of dosing and sampling times).

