9.2. Pharmacokinetic/Pharmacodynamic Relationships

Pharmacokinetic/Pharmacodynamic relationships will be analyzed for the PD analysis set. The exposure parameters AUC_{12h} and C_{trough} will be categorized into quartiles for Day 1, Day 3 and Day 5 (i.e.: after the last intake, this can be on Day 5, Day 6 or Day 7) (if available). Relationships of these parameters with the primary and selected secondary efficacy endpoints will be explored as follows.

The distribution of subjects over the hospital recovery scale on Day 6 will be tabulated per quartile for each exposure parameter for each PK timepoint.

The number and percentage of subjects with treatment-emergent adjudicated influenza complications will be tabulated for each quartile for each exposure parameter for each PK timepoint.

The Kaplan Meier estimates for the time to hospital discharge will be produced per quartile for each exposure parameter for each PK timepoint.

The Kaplan Meier estimates for the time from ICU admission to ICU discharge will be produced per each quartile for each exposure parameter for each PK timepoint.

The Kaplan Meier estimates for the time to return to daily activities will be produced per quartile for each exposure parameter for each PK timepoint.

The Kaplan Meier estimates for the time from start of mechanical ventilation to end of mechanical ventilation will be produced per each quartile for each exposure parameter for each PK timepoint.

The number and percentage of subjects readmitted to the hospital after the first discharge will be tabulated for each quartile for each exposure parameter for each PK timepoint.

Relationships of AUC_{12h} with safety will be explored as follows. The number and percentage of subjects with the following treatment-emergent adverse events by AUC_{12h} quartile for each PK timepoint will be tabulated:

- Any AE
- AEs of worst grade 3 or 4
- Deaths due to AE
- Serious AEs
- AEs for which study drug was permanently stopped
- AEs at least possibly related to study drug
- Confirmed diarrhea events

A frequency table of the worst treatment-emergent toxicity grades versus AUC_{12h} quartile will be presented for the laboratory parameters AST, ALT, and total bilirubin.

Separate frequency table will be produced for the worst treatment-emergent toxicity grades at each PK timepoint.

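### SAP 2.2.4 drops the protocol's ITT-i condition for PK data, so subjects without confirmed influenza A can enter the exposure-efficacy tables, which also carry no adjustment for baseline severity

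*SAP*

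**What the plan says.** Protocol 11.1 sets both populations. For PK: "Pharmacokinetic data will be evaluated on subjects in the ITT-i set who received pimodivir". For efficacy: "The efficacy endpoints will be analyzed on the Intent-to-Treat-infected (ITT-i) and by randomized treatment". SAP 2.2.2 repeats ITT-i as the efficacy set.

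SAP 2.2.4 words the PK set differently: "The PK analysis set is defined as subjects who have received at least 1 dose of pimodivir and have at least 1 valid blood sample". It has no infection criterion. SAP 2.2.5 builds on it: "The PD analysis set is defined as all subjects in the PK analysis set for whom at least one PK parameter could be derived". SAP 2.2.2.3 shows that treated subjects outside ITT-i are foreseen, because it defines a set of dosed subjects "who do not have a confirmed infection with influenza A".

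SAP 9.2 uses the PD set for all PK/PD work. Of the primary endpoint it says: "The distribution of subjects over the hospital recovery scale on Day 6 will be tabulated per quartile". It does the same for the six key secondary endpoints: counts for adjudicated complications and readmission, and Kaplan-Meier estimates for hospital discharge, ICU discharge, return to daily activities and end of mechanical ventilation. The quartiles are of AUC12h and Ctrough at Days 1, 3 and 5. No covariate or stratification by severity is named, and the set holds only pimodivir recipients.

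**The concern.** Two separate issues meet in these tables.

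The first is the population. The SAP departs from protocol 11.1 without giving a reason, and the departure carries over to efficacy outputs through the PD set. Protocol 11.1 does not define a PD set, so the conflict arises by inheritance from SAP 2.2.4. Subjects who were not infected would be expected to show little or no antiviral exposure-response and would pull any true relation towards the null.

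The second is comparability. Randomisation balances the arms, not the exposure quartiles within one arm. Protocol 3.2 ranks baseline severity and subject condition as the strongest predictors of outcome, and the primary model in SAP 5.2.3 adjusts for baseline hospital recovery scale (HRS) category and NEWS2. SAP 9.2 shows the same endpoint by quartile with neither. If exposure varied with severity, a raw table could suggest a harmful trend where there is none, or hide a real benefit. Protocol 11.9 makes further exposure-effect modelling depend on a visual trend, so a distorted raw picture could also decide whether that modelling is done.

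Exploring PK/PD for efficacy and safety is a stated secondary objective.

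**Working it through.** **Reproducing the plan's own figure.** The documents give no figure for the PD set, so the check starts from the sample size (Protocol 11.3). Inputs: Day 6 placebo distribution 30/30/25/5/5/5%, common odds ratio (OR) 0.62, two-sided 5%, 90% power, 1:1. The formula for ordered categories is N = 12(z_α + z_β)² / [(ln OR)² (1 − Σp̄³)], where p̄ is the mean of the two arms' category proportions.
- Pimodivir distribution implied by OR 0.62: 40.9/29.9/19.4/3.4/3.3/3.2%, so 1 − Σp̄³ = 0.918.
- N = 12 × (1.960 + 1.282)² / (0.2285 × 0.918) ≈ 601, and power at 600 is 89.9%. The stated 600 and 90% are reproduced.

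**Precision of a quartile contrast.** 300 / 4 = 75 subjects per quartile. SE of ln OR for 75 against 75 = 1/√[(150/12) × (1 − Σp³)] = 1/√(12.5 × 0.93) = 0.29. The 95% interval is a factor of exp(1.96 × 0.293) = 1.78 each way. Power to detect OR 0.62 is 37%.

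**Possible share outside ITT-i.** This trial's share is not given. The nearest guide is the phase 2 hospital study (FLZ2002). Protocol 1.1 reports complications on 63 + 32 = 95 subjects, and Protocol 1.4.4 gives 64 treated with pimodivir. The treated control group is inferred as 35, because 11.4% = 4/35 and 71.4% = 25/35 in the safety results. So 99 − 95 = 4 subjects, or 4.0%. In the pimodivir arm alone it is 64 − 63 = 1. The documents do not say why these subjects are missing from the denominators; lack of confirmed infection is an assumption. At 4%, 300 × 0.04 = 12 pimodivir subjects, about 3 per quartile.

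**Dilution.** Assume a true top-versus-bottom-quartile OR of 0.62 and no exposure effect in a share f of unconfirmed subjects. A common OR fitted to the mixture gives:

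| f | OR seen | share of ln OR kept |
|---|---|---|
| 1% | 0.623 | 99% |
| 2% | 0.626 | 98% |
| 5% | 0.635 | 95% |
| 10% | 0.651 | 90% |

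**Confounding, with no exposure effect at all.** Every input here is assumed.
- Two-level severity: OR for severe against mild 1.5 to 3, and severe share from 45% (bottom quartile) against 55% (top) up to 30% against 70%. False OR for a worse Day 6 score in the top quartile: 1.04 to 1.53. Under the same inputs, a true OR of 0.62 would appear as 0.65 to 0.97.
- Continuous severity: correlation with log AUC 0.2 to 0.4, ln OR per SD of severity 0.7 to 1.0. Simulated false OR: about 1.4 to 2.4. Hand check: mean log AUC differs by 2.54 SD between the outer quartiles, so 2.54 × 0.2 × 0.7 = 0.36 (OR 1.43) and 2.54 × 0.4 × 1.0 = 1.02 (OR 2.76). The fitted marginal values are somewhat lower, as expected.

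Together these give about 1.04 to 2.4.

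**The case against.** **Dilution is negligible.** This stands. A move from 0.62 to 0.651 at most is invisible beside an interval of a factor of 1.78. Some unconfirmed subjects may also have been infected: under SAP 2.2.2.1 a locally positive subject is unconfirmed if the central baseline PCR is negative and fewer than two later central PCRs are positive. The assumed zero effect therefore gives a ceiling for the attenuation.

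**A much larger share might be inferred from the community study.** Its figures are 285 − 64 + 71 = 292 treated and 223 confirmed, so 69, or 24%, were outside the efficacy set. That was outpatient, uncomplicated influenza, and the documents do not describe its entry test. Protocol 4.1 here requires a positive molecular test. SAP 2.2.2.2 still words that criterion to allow a rapid influenza diagnostic test, and SAP 4.1 lists an antigen assay category, so the safeguard is not watertight. The 24% still does not transfer.

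**A reader might infer that exposure rises with illness.** The safety margins in Protocol 1.4.4 fall when hospital-study exposures are used (41/17 = 2.4, 24/10 = 2.4, 2/0.7 = 2.9, 4/1.6 = 2.5). This contrasts the hospital study at steady state with a reference whose population and sampling day are not given. It shows nothing about severity and exposure among hospitalised subjects. The one within-hospital contrast reported, elderly against non-elderly (Protocol 1.1), found comparable PK.

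**Modelling is already foreseen.** Protocol 9.4.4 and 11.8 test covariates on PK, and 11.9 allows exposure-effect models in a separate report. This stands in part: the exposure-effect models are conditional on a visual trend, and severity is not named as a covariate.

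**A placebo row is a preference.** This stands. It would give a reference level, but placebo results are reported elsewhere and the row would not remove confounding between quartiles.

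**Conclusion.** The population mismatch is certain on the text: SAP 2.2.4 omits a condition that protocol 11.1 sets, 2.2.5 inherits it, and 9.2 applies the result to the primary and six key secondary endpoints. Its likely numerical effect is small, with an OR of 0.62 becoming 0.623 to 0.651 at 1% to 10% unconfirmed.

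The lack of severity adjustment matters more, but it is a risk rather than a finding. A reader might conclude that the exposure-efficacy results are diluted and confounded. The documents support only that they can be: no count of unconfirmed pimodivir subjects is given, and neither the existence nor the direction of a link between severity and exposure in this population is shown. The range of 1.04 to 2.4 reflects the assumptions chosen, from almost nothing to a substantial false trend.

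The tables are exploratory and carry no test. The primary analysis, the confirmatory hierarchy and the safety conclusions are unaffected. The case for acting is that the objective is stated in the protocol and the remedy is cheap.

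**What to change.** - In SAP 9.2, restrict every exposure-efficacy output to PD-set subjects who are in ITT-i, or state why the plan departs from protocol 11.1. Keep all dosed subjects with a derived PK parameter for the exposure-safety outputs.
- Add one proportional odds model of Day 6 HRS on AUC12h quartile, adjusted for baseline HRS category and NEWS2. Name the PK time point. Day 1 or Day 3 exposure precedes the outcome, whereas SAP 9.1 lets the exposure labelled Day 5 come from an intake as late as Day 7.
- Optionally, add a placebo ITT-i reference row, with a note that it does not address confounding between quartiles.

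The cost is a change of SAP wording, one filter and one extra model. The efficacy tables would lose a few subjects, about 12 of 300 if the 4% from the hospital study applied.
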